Pilot, randomized trial of the use of pediatric size phlebotomy tubes in adult critically ill patients to reduce red blood cell transfusions

NCT03286465

Version Date: 09/28/2017

Protocol Title: Pilot, randomized trial of the use of pediatric size phlebotomy tubes in adult critically ill patients to reduce red blood cell transfusions

Principal Investigator: [name] [name]

Co-Investigators: [name]; [name]; [name]; [name]

Study Coordinator: None

Population: Adult, intensive care unit patients, newly admitted to the ICU. N=200

Number of Sites: Single site / Memorial Hermann Hospital / Medical ICU, Transplant ICU

Intervention: Pediatric size phlebotomy tubes

Comparison: Adult size phlebotomy tubes

Outcomes: Primary: Time to red blood cell transfusion or hemoglobin less than 7 g/dL
Main secondary: Rate of change in hemoglobin (g/dL per patient per day)

Study Duration: 6-12 months

Subject Duration: Duration of ICU stay, up to 30 days

1. BACKGROUND AND RATIONALE

Anemia and red blood cells (RBC) transfusions are common in critically ill patients.^{1,2} One factor associated with the development of anemia^{3,4} and RBC transfusions^{5,6} in these patients is the volume of diagnostic phlebotomy. Therefore, a more efficient use of blood drawn for diagnostic testing has the potential to reduce transfusions.

Even though blood conserving strategies could be beneficial, there are no randomized controlled trials (RCTs) assessing their efficacy in reducing RBC transfusions in adults. A blood conserving arterial line system reduced the RBC transfusion volume in an RCT of very low birth weight infants.⁷ However, the results of this trial might not be applicable to adults as their larger circulating blood volume might limit the benefit of any blood conserving intervention.⁸

The use of pediatric size phlebotomy tubes has been proposed to reduce anemia and RBC transfusions in adults. Adult phlebotomy volumes exceed pediatric ones for the same tests.⁹ However, the absence of high quality data supporting their efficacy compounded by the loss of automation in the processing of pediatric tubes prevents their routine use. Two RCTs assessed their effect on the change in hemoglobin in adults. The first trial showed no benefit, but the intervention was limited to basic metabolic profile tubes and the study was conducted in a general Internal Medicine population.⁸ The second trial, performed in the Intensive Care Unit (ICU) setting, demonstrated a reduction in the decline of

hemoglobin, but used a co-intervention.¹⁰ None of these studies analyzed the change in hemoglobin as a function of time at risk.

An RCT is needed to evaluate the hypothesis that the use of pediatric size phlebotomy tubes reduces RBC transfusions in adult ICU patients compared with the use of adult size tubes. However, its design is complicated by the lack of knowledge regarding the expected effect size and overall feasibility of this intervention. Thus, we will perform a pilot RCT that will allow us to investigate these issues.

2. OBJECTIVES

2.1 Primary

Estimate the effect size of using pediatric phlebotomy tubes in ICU patients on RBC transfusions compared with the use of adult phlebotomy tubes during their ICU stay

2.2 Secondary

- Determine the rate of recruitment of participants
- Evaluate the feasibility of implementing phlebotomies using pediatric size tubes in an adult ICU
- Establish the rate of change of hemoglobin in the intervention and control groups
- Identify the ICU admission hemoglobin range that best predicts benefit from pediatric phlebotomy tubes

3. METHODS

3.1 Trial design

Randomized controlled trial

3.2 Participants

Inclusion (all of the following)

- Age \geq 18 years old
- New admission to the medical or transplant ICU at Memorial Hermann Hospital in Houston
- ICU admission hemoglobin level of at least 7 g/dL. The ICU admission hemoglobin will be the most recent hemoglobin value available at the time of screening for inclusion in the study.
- Randomization is expected within 12 hour of admission to the ICU

Exclusion (any of the following)

Conditions that affect the generation or loss of RBCs

- Clinical bleeding. Defined as menstrual bleeding, bleeding leading to a change in the frequency of hemoglobin monitoring or to an order for a medication, transfusion, procedure, or consultation intended to prevent or treat bleeding.
- Known hemolytic disorder (e.g. sickle cell disease, hereditary spherocytosis, autoimmune hemolytic anemia)
- Bone marrow disorder (e.g. aplastic anemia, marrow infiltration disorder, chemotherapy within the last 8 weeks)

Randomization to adult size phlebotomy tubes is not recommended

- Jehovah's Witnesses

Collection of blood tests is not possible or desired

- Patient is comfort care measures only

Inability to complete the desired time of follow up

- Refractory shock: mean arterial blood pressure below 60 mmHg despite maximal doses of 3 vasopressors. Maximal dose of vasopressors are as follows: Norepinephrine 70 mcg/min; vasopressin 0.04 units/min; epinephrine 35 mcg/min; dopamine 20 mcg/kg/min; phenylephrine 350 mcg/min
- Severe acidosis: pH below 7 in more than one arterial blood gas within 24 hours of ICU admission in the absence of diabetic ketoacidosis

Other

- Surgical admission diagnosis
- Pregnancy
- Current prisoner

33 Allocation

All patients admitted to the medical or transplant ICU will be screened for eligibility. Group assignment will be done using the randomization module in the Research electronic data capture (RedCap). Randomization will be stratified by ICU admission hemoglobin level (7 to 9.49 g/dL, 9.5 to 11.99 g/dL, and 12 g/dL or greater). Patients will be randomized using permuted blocks of 4 or 6 and a 1 to 1 ratio, into one of two groups: the pediatric size phlebotomy tubes group or the adult size phlebotomy tubes group.

34 Interventions

Pre-intervention period (1 month)

The first objective of this period is to standardize the pediatric tubes phlebotomy process. Study procedures will be presented to the ICU nurses by email, printed material, and lectures. Information will include the type of pediatric tube and the blood volume needed for each test, and the importance to collect only the total estimated blood volume according to the tests that need to be performed. Pocket size cards that include the suggested volume of blood to be drawn for each pediatric tube will be provided. No guidance regarding the phlebotomy process when using adult size tubes will be given so that it reflects usual practice. The volume of fluid

drawn to clear the intravenous line will be returned to the patient in a sterile fashion in both groups whenever possible. The frequency and type of blood tests performed will follow usual practice.

The second objective of the pre-intervention period is to provide RBC transfusions recommendations to the ICU physicians. This will be accomplished by email and during any of the regular Critical Care Division meetings. An RBC transfusion will be recommended if the hemoglobin is less than 7 g/dL or if there is bleeding with associated hemodynamic instability regardless of the hemoglobin level. It will be dependent upon the ICU physician to make the final determination regarding the need of any transfusions.

Intervention period (5-11 months)

Blood tests will be collected using pediatric and adult phlebotomy tubes in the experimental and control groups, respectively (Table 1). Arterial blood gases, blood cultures, and lactate levels will be collected using the same tubes in both groups. The exposure period will be from randomization until the hemoglobin is less than 7 g/dL, an RBC transfusion order is placed, the patient is discharged from the ICU (time of an acceptance note) or dies (time of death), clinical bleeding or surgery occur, comfort care measures only are initiated, or the patient stays in the ICU for more than 30 consecutive days.

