3.5 Outcomes

Primary

The primary outcome will be the time from randomization to hemoglobin less than 7 g/dL or RBC transfusion order.

Secondary

The main secondary outcome will be the rate of change in hemoglobin (g/dL/patient/day) in the ICU. This will be calculated as the most recent hemoglobin prior to randomization minus the last hemoglobin prior to ICU discharge, death, RBC transfusion, clinical bleeding, surgery, or change of clinical status to comfort measures, divided by the number of days (rounded to the nearest 0.5) between these two values (crude estimate). If the longitudinal measures of hemoglobin levels deviate substantially from a linear trajectory, we will use a growth model to capture the best fitting function of time (see Analysis Plan for details) and generate a predicted rate of change.

Other secondary outcomes will be the proportion of participants receiving an RBC transfusion while in the ICU, the proportion of patients with at least one inadequate blood sample for laboratory analysis, and the ICU mortality. An inadequate blood sample is defined as any blood sample that requires recollection.

The patient's admission height and weight will be used to estimate the total blood volume of each patient based on Nadler's equation.¹¹ The total daily phlebotomy volume per participant will be calculated based on the number of blood tests per patient per day and the minimal blood volume for analysis of each test.

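### Eligibility and stratum are judged on hemoglobin at screening but the event clock starts at randomization, so the written criteria can admit a patient already below 7 g/dL when follow-up begins

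*Combined protocol and SAP*

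**What the plan says.** Three parts of the combined protocol and SAP bear on this.

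- **Entry and stratum (section 3.2 and the Allocation section).** The inclusion rule is "ICU admission hemoglobin level of at least 7 g/dL", and the value meant is specified: "The ICU admission hemoglobin will be the most recent hemoglobin value available at the time of screening for inclusion in the study". The same quantity defines the three randomization strata, the lowest running from 7 to 9.49 g/dL. On timing, the section says only "Randomization is expected within 12 hour of admission to the ICU".
- **Primary outcome (section 3.5).** "The primary outcome will be the time from randomization to hemoglobin less than 7 g/dL or RBC transfusion order".
- **Main secondary outcome (section 3.5).** The rate of change starts from "the most recent hemoglobin prior to randomization", which is a different anchor from the screening value.

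Section 3.7 puts the stratum into both the Cox model and the slope regression, and analyzes by intention to treat. Its censoring list has no entry for a patient whose hemoglobin crossed 7 g/dL before randomization. The bleeding exclusion in section 3.2 does not reach a patient whose hemoglobin drifts down without bleeding.

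**The concern.** The entry limit and the event limit are the same number, seen from opposite sides. That works only if both are applied at the same moment, and here they are not. Take a patient with 7.4 g/dL at screening and 6.8 g/dL on a later sample taken before randomization. Every written criterion is met, yet the patient is below the event threshold when follow-up opens. The same holds for a non-bleeding patient for whom red cells are ordered in that interval.

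Tube size cannot have caused such an event, because no blood has yet been drawn into assigned tubes. These events should fall equally in both arms and move the hazard ratio toward 1. Section 2.1 makes estimation of the effect size the primary objective, and section 1 gives the unknown effect size as a reason for running a pilot, so the dilution acts on the quantity the trial is meant to supply. Affected patients would most likely sit in the lowest stratum, which also touches the section 2.2 objective of finding the admission hemoglobin range that benefits.

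**Working it through.** **1. The passages side by side.**

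| Item | Hemoglobin or time used | Source |
|---|---|---|
| Entry limit, at least 7 g/dL | latest value at screening | 3.2 |
| Randomization stratum | same screening value | Allocation, 3.2 |
| Start of primary clock | randomization | 3.5 |
| Event limit, below 7 g/dL, or red cell order | after randomization | 3.5 |
| Slope baseline | latest value before randomization | 3.5 |

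Nothing ties the first two rows to the last three. The Interventions section ends exposure once hemoglobin is below 7 g/dL. Read literally, a patient already there at randomization has no exposure period but stays in the analysis under intention to treat. That section also recommends transfusion below 7 g/dL, so a red cell order or a repeat low value soon after randomization is likely.

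**2. Inputs from the plan.** 100 patients per arm, 1:1 allocation, control event rate 20-40%, follow-up up to 30 days (sections 1, 3.7 and Allocation). The plan's one precision figure, +/- 8% per group, reproduces at the low end: 1.96 x sqrt(0.20 x 0.80 / 100) = 0.078. At 40% it is 1.96 x sqrt(0.40 x 0.60 / 100) = 0.096. The present point does not depend on that figure.

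**3. Assumptions, because the plan gives no value.** True hazard ratio 0.50 or 0.70. A share f of each arm is counted as an event at time zero. Event times are exponential; censoring is exponential at 0.2 per day (mean 5 days) with a 30-day cap. The total control event rate, including time-zero events, is held at 20% or 40%.

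**4. Calculation.** A Cox model was fitted to 400,000 simulated patients per arm, with and without the time-zero patients. The difference in log hazard ratio was divided by the standard error expected with 200 patients, SE = 2 / sqrt(events).

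| Control rate | True HR | f = 1% (2 of 200) | f = 2% (4 of 200) | f = 5% (10 of 200) |
|---|---|---|---|---|
| 20% | 0.50 | 0.52 (0.13 SE) | 0.55 (0.26 SE) | 0.62 (0.63 SE) |
| 20% | 0.70 | 0.72 (0.06 SE) | 0.72 (0.12 SE) | 0.77 (0.31 SE) |
| 40% | 0.50 | 0.51 (0.09 SE) | 0.52 (0.18 SE) | 0.56 (0.43 SE) |
| 40% | 0.70 | 0.71 (0.04 SE) | 0.71 (0.09 SE) | 0.74 (0.20 SE) |

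With f = 0 the fitted ratio returns to the assumed one.

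**5. Hand check.** With f = 5% and a 20% control rate, 5/20 = 25% of control events are at time zero. Giving these a ratio of 1 yields 0.25 x 1 + 0.75 x 0.70 = 0.775, against 0.77 simulated. At a 40% control rate the share is 5/40 = 12.5%, and 0.125 + 0.875 x 0.70 = 0.7375, against 0.74.

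**6. Scale.** At a 20% control rate and a true ratio of 0.70, about 34.7 events are expected, so SE = 2 / sqrt(34.7) = 0.34. The 95% interval around 0.70 then runs from about 0.36 to 1.36. A shift to 0.72 is small against that.

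**The case against.** The strongest reply is that the interval in question may be very short. The 12 hours run from ICU admission to randomization, not from screening to randomization. Section 6 describes screening by review of the electronic record, with a waiver of consent being sought, and assignment is made in the study database. No stated step need separate the two, so the screening value and the last value before randomization may usually be the same. The red cell order route is narrower still: clinical bleeding is excluded and transfusion is otherwise recommended only below 7 g/dL, although the physician keeps discretion. The bias is also conservative and cannot create an apparent benefit. All of this stands, and it limits the size of the problem. It does not close the gap in the text.

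Four stronger readings are tempting and are not supported.

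- *A low value before randomization is itself a primary event.* No section says so; the outcome is timed from randomization. The patient would more likely register on the next sample or order. If the software dropped records with zero follow-up time there would be no dilution, but that would conflict with intention to treat.
- *No event on the first hemoglobin after randomization can reflect tube size.* Test type and frequency follow usual practice, so other tests may already have been drawn in assigned tubes.
- *A large share of events is early, so a definitive trial planned on this pilot would be far too large.* The documents give no early share from which to argue this.
- *Different anchors for stratum and slope baseline are an error in themselves.* Adjusting for the stratum as randomized is standard practice. Using one value is tidier, but the present arrangement does not invalidate the regression.

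**Conclusion.** The point holds as a gap in the eligibility rule. As written, sections 3.2 and 3.5 allow a non-bleeding patient to enter with hemoglobin already below 7 g/dL, or with red cells already ordered, and to become an event at or soon after time zero regardless of assignment. The effect is attenuation toward a hazard ratio of 1 when a true effect exists, and no bias when there is none.

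The size is unknown, because the documents give neither the screening-to-randomization interval nor the affected share. Under the assumptions above, 1-2% of patients shifts the log hazard ratio by about 0.04-0.26 SE, which is minor against the pilot's imprecision; 5% shifts it by about 0.2-0.6 SE, which is worth avoiding. The case for acting is that the pilot exists to estimate this effect, a larger sample does not remove the attenuation, and the correction is nearly free.

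**What to change.** In section 3.2, redefine the ICU admission hemoglobin as the last hemoglobin before randomization. Require it to be at least 7 g/dL, with no red cell order placed since that sample. Use this one value for the stratum and for the slope baseline, which section 3.5 already anchors there.

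The cost is one further look at the record when randomization is run, and a few screened patients who become ineligible. The sample size stays at 200 and the primary analysis is unchanged.

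A supplementary Cox model that removes early events is not needed for this fix. It would select patients on what happens after randomization and could discard events that the assigned tubes had already influenced.

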3.5 Outcomes

Primary

The primary outcome will be the time from randomization to hemoglobin less than 7 g/dL or RBC transfusion order.

Secondary

The main secondary outcome will be the rate of change in hemoglobin (g/dL/patient/day) in the ICU. This will be calculated as the most recent hemoglobin prior to randomization minus the last hemoglobin prior to ICU discharge, death, RBC transfusion, clinical bleeding, surgery, or change of clinical status to comfort measures, divided by the number of days (rounded to the nearest 0.5) between these two values (crude estimate). If the longitudinal measures of hemoglobin levels deviate substantially from a linear trajectory, we will use a growth model to capture the best fitting function of time (see Analysis Plan for details) and generate a predicted rate of change.

Other secondary outcomes will be the proportion of participants receiving an RBC transfusion while in the ICU, the proportion of patients with at least one inadequate blood sample for laboratory analysis, and the ICU mortality. An inadequate blood sample is defined as any blood sample that requires recollection.

The patient's admission height and weight will be used to estimate the total blood volume of each patient based on Nadler's equation.¹¹ The total daily phlebotomy volume per participant will be calculated based on the number of blood tests per patient per day and the minimal blood volume for analysis of each test.

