3.7 Analysis plan

Baseline variables (e.g. gender, race, age) between groups will be examined for clinically significant differences that may have occurred by chance. If a clinically significant difference is noted, both unadjusted and adjusted analyses will be performed.

Intent-to-treat analyses will be used. The primary outcome will be assessed using time to event analysis with the Cox proportional hazard model including treatment group and ICU admission hemoglobin level group (stratifying variable). Censoring events will be death, ICU discharge, clinical bleeding, surgery, initiation of comfort care measures, and end of the study. We will report the hazard ratio and 95% confidence interval (CI).

We will assess whether the longitudinal measures of hemoglobin follow a linear trajectory. If they substantially deviate, we will employ multilevel mixed models including a quadratic term for time or splines to capture the non-linear change while accounting for within-subject correlation. We will generate predicted rates of change to compare between the study groups.

To compare the rate of change in hemoglobin (either crude or predicted) between the two study groups, a linear regression model will be used with treatment and ICU admission hemoglobin groups as covariates. Multiple regression analysis will be used to assess the relationship between the rate of change in hemoglobin as the dependent variable, and age, admission hemoglobin, acute physiology and chronic health evaluation (APACHE) II score, acute or chronic renal disease, sepsis admission diagnosis, use of medications that can cause bleeding, intervention group, and ICU admission hemoglobin group as independent variables. Proportions of RBC transfusion and proportions of at least one inadequate blood sample will be compared among the two groups using logistic regression models with treatment group and ICU admission hemoglobin level group as covariates.

Sample Size

It is estimated that the primary outcome will occur in about 20-40% of the participants in the control group.^{1,2,6,12-14} A total of 200 patients (100 in each group) will be randomized in the study. This number of participants was chosen to allow completion of the study in a reasonable time frame while obtaining preliminary information to estimate an unbiased treatment effect. This sample size allows a reasonable width of the 95% CI for the rate of the primary outcome in each group (+/- 8%).

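### The crude hemoglobin rate is divided by time that starts before randomization, so under a constant daily tube effect the between-arm difference is pulled toward zero

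*Combined protocol and SAP*

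**What the plan says.** Section 3.5 (Outcomes, Secondary) defines the rate of change in hemoglobin from two values per patient: "This will be calculated as the most recent hemoglobin prior to randomization minus the last hemoglobin prior to ICU discharge", with death, transfusion, clinical bleeding, surgery and comfort measures as the other end events. The change is then "divided by the number of days (rounded to the nearest 0.5) between these two values (crude estimate"). Both numerator and denominator therefore begin at a draw taken before randomization.

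Section 3.4 (Interventions, intervention period) sets the clock for the tubes themselves: "The exposure period will be from randomization until the hemoglobin is less than 7 g/dL" or another end event occurs. Section 3.2 says "Randomization is expected within 12 hour of admission to the ICU". It also says of the eligibility value: "The ICU admission hemoglobin will be the most recent hemoglobin value available at the time of screening for inclusion in the study". No maximum age is given for that value.

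Section 3.7 compares the rates between arms: "a linear regression model will be used with treatment and ICU admission hemoglobin groups as covariates". It has no weight or offset for exposed time. If the course is substantially non-linear, section 3.5 says "we will use a growth model to capture the best fitting function of time", and predicted rates are compared instead. The time origin of that model is not stated. The primary outcome, in the same section 3.5, is timed from randomization.

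**The concern.** The two main outcomes run on different clocks. The primary outcome starts at randomization, when assignment can first have an effect. The hemoglobin rate starts earlier, by an interval that the plan does not limit. Any difference between arms can build up only after randomization, but it is spread over the longer interval.

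This matters because the pilot is meant to inform a later trial. Section 1 justifies it by the unknown effect size and notes that earlier trials did not relate hemoglobin change to time at risk. Section 3.7 says the sample is meant to support an unbiased treatment effect. Section 2.2 makes the rate of change in each group an objective. A shrinkage that depends on how fast this site randomizes and how long its patients stay would not carry over to another setting. The rate in each arm also mixes any change before randomization with change on assigned tubes.

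**Working it through.** **Inputs from the documents.** The start and end values and the denominator are in section 3.5, the start of exposure in section 3.4, the expected 12 h from ICU admission to randomization in section 3.2, and the unweighted regression in section 3.7. Follow-up is "Duration of ICU stay, up to 30 days" (title-page synopsis). The documents give no expected ICU stay, draw schedule or gap from draw to randomization, and no effect size or SD for the rate. There is thus no stated figure to reproduce.

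**Formula.** Let u be days from baseline draw to randomization, T days from randomization to the last hemoglobin, and d a constant between-arm difference in g/dL/day that acts only after randomization. Take u and T as similarly distributed in the two arms. The tube effect adds d × T to the numerator, and the denominator is u + T. A patient's contribution to the crude difference is therefore d × T/(u+T), a proportional loss of u/(u+T).

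**Direct values of u/(u+T).** Example: u = 12 h = 0.5 day and T = 3 days give 0.5/3.5 = 14.3%.

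| u | T = 1 d | 2 d | 3 d | 5 d | 7 d | 10 d | 30 d |
|---|---|---|---|---|---|---|---|
| 2 h | 7.7% | 4.0% | 2.7% | 1.6% | 1.2% | 0.8% | 0.3% |
| 6 h | 20.0% | 11.1% | 7.7% | 4.8% | 3.4% | 2.4% | 0.8% |
| 12 h | 33.3% | 20.0% | 14.3% | 9.1% | 6.7% | 4.8% | 1.6% |
| 24 h | 50.0% | 33.3% | 25.0% | 16.7% | 12.5% | 9.1% | 3.2% |

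The 24 h row is included because the 12 h in section 3.2 is an expectation measured from ICU admission. The baseline draw may be more recent than admission or may predate it.

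**Average over an assumed ICU population.** Assumptions: an admission draw plus one morning draw a day, randomization 1-12 h after ICU admission, and a log-normal stay with log-SD 0.8. The mean gap is about 5 h. The average of u/(u+T) over patients is given below; ranges reflect details that the scenario leaves open.

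| Median stay | Randomized at 1-12 h | Randomized at 6-12 h |
|---|---|---|
| 2 days | 17-19% | 23-24% |
| 3 days | 12-13% | 17% |
| 4 days | 9-10% | 13% |
| 6 days | 6% | 8-9% |

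Rounding the denominator to 0.5 day changes these figures by less than 1 point. The regression in section 3.7 counts each patient equally, so short stays weigh fully. Pooled pre-randomization time as a share of pooled total time would be only 9%, 6%, 4.5% and 3% in the 1-12 h case.

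**Effect on the estimate.** In 400 simulated trials of 200 patients (true difference 0.10 g/dL/day, control slope -0.30, within-patient SD 0.3, no fluid-related fall), the crude rule averaged 0.078, 0.084, 0.090 and 0.092 at median stays of 2, 3, 4 and 6 days. A mixed model with treatment acting on time since randomization averaged 0.098, 0.098, 0.100 and 0.100.

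**Restarting the two-point denominator.** With u uniform on 0-12 h, median T of 3 days (log-SD 0.7), a true difference of 0.10 and 100 per arm, dividing by time from randomization moves the loss from 8.2% to -1.2%. It also raises the SD of the rate from 0.33 to 0.39 and lowers power from 0.51 to 0.45.

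**The case against.** The strongest reply is that the crude rate is coherent as defined. It is a rate in the ICU, with numerator and denominator over the same interval, and a pre-randomization baseline is sound practice. This stands as far as the baseline goes. As a description of each arm the rate is usable. As an estimate of the daily tube effect it is diluted.

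A second reply is that the size depends on the model. Phlebotomy loss comes in steps: tube size acts only when blood is drawn, and the loss from the last sample cannot show in that sample's own hemoglobin. If the effect accrues per draw on the same assumed schedule, the crude rule falls short by about 39% at a 3-day median stay, and a clock started at randomization still falls short by about 34%; at 6 days the figures are 20% and 16%. This stands. It also means that the mixed model's near-perfect recovery above is partly built in, because the data were generated under the model that was fitted.

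A third reply is that the growth model may take over. It does so only if the course is substantially non-linear. Because its time origin is unstated, the bias is neither shown nor excluded there.

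A reader might also infer that the arms used identical tubes before randomization. Section 3.4 implies this but does not state it. The argument does not need it: assignment cannot affect what happened before it was made, and randomization balances earlier practice in expectation.

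**Conclusion.** The concern holds for the crude two-point rate. Under a constant daily tube effect the between-arm difference is biased toward zero by the average of u/(u+T). The direction follows from the plan's own definitions; the size does not. Under the assumptions above it is about 6% to 19% for median stays of 6 down to 2 days, and about 8% to 24% if randomization falls at 6-12 h. The direct range over u = 2-24 h and T = 1-30 days is 0.3% to 50%. Effects that accrue per draw would change these figures.

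Three stronger readings are tempting and are not supported. First, no single percentage can be presented as a property of the plan, because the documents give neither the gap nor the stay. Second, the pilot's main effect-size objective (section 2.1, transfusions) is not undermined, because the primary outcome is timed from randomization. Third, this is not a type I error problem or a demonstrated loss of power: the early clock also shrinks the SD, and in the assumed simulations power was slightly higher with the denominator as written. What is at stake is the size of the main secondary estimate, which the plan should correct before analysis.

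**What to change.** Keep the pre-randomization hemoglobin as baseline. Make the between-arm slope comparison a mixed model on all recorded hemoglobin values, with a common course before randomization and treatment acting on time since randomization (zero before it). Use it whether or not the trajectory is linear, and state the same time origin for the quadratic or spline branch. Report the rate in each arm per day since randomization. Show the two-point rate only as a descriptive figure, labelled as including pre-randomization time, with the baseline-to-randomization gap reported by arm. Do not simply restart the two-point denominator at randomization, which makes the rate noisier.

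The cost is SAP wording and modest analysis work; draw times and randomization time are already needed for the planned outcomes. There is a small downside: the slope becomes model-based and gives more weight to longer stays. In simulations at a 3-day median stay the SD of the estimated difference fell from 0.058 to 0.047 under one set of assumptions and from 0.053 to 0.033 under another. Most of that gain comes from using all values, not from the change of clock.
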